### **13.C. Stakeholder Advisory Board**

The SAB will consist of representatives from the organizations listed above. These advisors will be consulted in smaller sub-groups for specific feedback on study design, study progress, and dissemination throughout the life of the project. We want to ensure our study remains responsive to the needs and priorities of these stakeholders, so the research remains practical and relevant when study funds no longer support this work.

Specifically we aim to gather formal input from:

- Clinical stakeholders (physicians, nurses, clinic administration)
- Health plan stakeholders (supplying telemonitoring equipment)
- IS&T stakeholders (supporting Epic and other technical needs for the project)
- External stakeholders (our vendors, professional organizations like American Heart Association, etc)

We will meet with each of these groups of stakeholders on an ongoing basis, and compile twice annual reports to PCORI about stakeholder input and response to our project. Groups of stakeholders will be brought together for joint discussions as needed to gather the type of input that would benefit from diverse viewpoints. Stakeholder Advisors are not compensated for their participation in these meetings, as they are primarily professional colleagues.

## **14. Human Subjects Protection**

### **14.A. Protected Health Information and sources of data**

All necessary data to determine study eligibility, conduct the study interventions, and test the study hypotheses among n=2000 enrolled patients are derived from (a) the EHR, (b) health plan pharmacy claims, and (c) surveys of eligible patients in both study arms. Limited EHR data will include demographics, vital signs, orders, diagnoses, encounters, and laboratory data for specified periods.

Among a smaller group of consenting participants, we will collect focus group data on their experiences receiving BP care. Additional qualitative data will be collected using field observations in clinics, short surveys and interviews with

pharmacists and physicians. These data will be used to assess the impact of study interventions on outcomes. A detailed description of the inclusion and exclusion criteria for study subjects can be found in section 4.c. We anticipate accessing up to 5000 patient records to achieve n=2000 enrolled patients.

#### **14.B. Potential risks to subjects**

Potential risks to subjects relate to the treatment of hypertension and consist principally of adverse events related to medications, which can potentially be severe or even fatal. However, all treatment in the study in both intervention groups is evidence-based and limited to FDA-approved treatment. Although patients in the telehealth group may be treated with greater numbers and higher doses of antihypertensive therapy, previous telehealth trials with pharmacist or nurse management have not reported greater adverse events in the telehealth group. In the previous telehealth trial conducted by this research team there were several more episodes of hypotension in the telehealth group than in the usual care group, although this difference was not statistically significant. All such episodes occurred in patients with diabetes or kidney disease who had a lower BP treatment goal (<130/80 mm Hg) than is the goal in this study (<140/90 mm Hg). Therefore, the risks of participating in the study are considered minimal and no greater than those incurred through routine treatment of hypertension. We have described below the methods used to minimize this risk.

Additional risks to patients are also minimal and include principally the risk of violation of confidentiality. Measures to minimize these risks are also discussed below.

Study participants may choose alternative treatments and procedures with their treating clinician. Participants in the telehealth group are free to decline telemonitoring or any component of the telehealth care intervention.

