### **7.C. Aim 1 other outcomes**

Other clinical outcomes include cardiovascular risk factors other than systolic BP (DBP, lipid levels, statin use, antihypertensive medication use, smoking, and overall cardiovascular risk based on 10-year AHA/ACC pooled risk equations and the Framingham 30-year risk equation that may be influenced directly or indirectly by telehealth care relative to clinic-based care. The study will also monitor laboratory abnormalities in electrolytes and kidney function that may be affected by hypertension medications, as well as low blood pressure (hypotension) and fainting that might result from overly aggressive blood pressure lowering. All secondary clinical outcome values and dates are routinely documented in the EHR as they are measured at clinic encounters or are returned as laboratory values.

The patient survey will also include some items and scales that do not meet the criteria for secondary outcomes but have been identified by patients or investigators as potentially important, as well as all responses from the 12 and 24 month surveys.

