## **8. Measurements**

### **8.A. EHR for clinical measures**

The primary outcome, SBP, and other clinical outcomes will be extracted from data documented in the electronic health record (EHR). An EHR tool that operates in HealthPartners primary care clinics is automatically triggered when vital sign

data are saved to the EHR. The tool searches the EHR to gather the most recent vital signs (e.g., SBP, DBP) and laboratory values (e.g., total cholesterol, LDL, potassium, sodium, creatinine), current medications (e.g., antihypertensive medications, statins), lifestyle data (e.g., smoking status, BMI), safety events (hypotension, fainting), and socio-demographic information (e.g., age, ethnicity, race). These data elements are used to calculate total cardiovascular risk (e.g., 10 year Hard CV risk via the ACC/AHA risk model; 30 year lifetime risk via the Framingham model) and to alert the provider to abnormalities (e.g., potassium, sodium, creatinine values that are out of range). The EHR tool documents the information that was aggregated for each triggering event, including the dates that were associated with each data element (e.g., date of cholesterol test). The tool also assigns a random unique identifier to each patient so that data elements stored in the EHR as part of routine care may be readily extracted and re-assembled to describe within-person changes in clinical outcomes over time.

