#### **14.C.2. Protection of safe medical treatment**

All hypertension care provided in the study follows evidence-based guidelines and HealthPartners policies and procedures for high-quality care. All staff affected by the study will receive appropriate training, either through HealthPartners or by the study team (see section 6). MTM Pharmacists in the telehealth clinics will use an established protocol for managing hypertension and other CV risk factors, in accordance with long-standing HealthPartners policy

and their collaborative practice or supervisory agreements with clinic physicians (see appendices A-C for evidence-based treatment guidelines)

The study will monitor for adverse effects of study interventions by extracting EHR laboratory data on potassium, sodium, and kidney function, and diagnoses for hypotension and fainting (see section 15 about data safety and monitoring)

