self-reports of these outcomes from patient surveys. Similar to the clinical effectiveness analyses, patient reported outcomes (PROs) will be collected at enrollment and then 6, 12 and 24 months later but the contrast of interest is the enrollment to 6 month change among telehealth care relative to clinic-based care patients. Missing values resulting from non-consent, non-response, loss to follow-up and item non-response increase the likelihood of misestimating PRO models. The patient survey sampling frame will include a wealth of demographic and clinical information so that we can identify characteristics that are associated with each source of missingness and develop a plan for handling missing data (e.g., multiple imputation).

4.3 Equity of patient benefit. The clinic-based care and telehealth care intervention have both been shown effective in improving hypertension outcomes. The purpose of this work is to estimate their relative effectiveness in improving clinical and patient reported outcomes. It is not expected that either of these approaches will be sufficiently superior to the other to warrant developing stopping rules for clinical benefit. Similarly, the anticipated effect sizes are sufficiently modest and accrue over a time frame such that stopping the trial early for futility would more likely result in a Type II error than offer patients a more beneficial alternative treatment.

4.4 Safety outcomes monitoring. Both interventions have been implemented in primary care settings or systematically studied with no evidence of increased likelihood of risk to patients. It is possible nonetheless that incident diagnoses related to hypertension and antihypertensive medications (e.g., hypotension / fainting, electrolyte disturbances, renal failure) and changes in lab measures indicative of antihypertensive medication (e.g., Na, K, eGFR) may be more evident among patients in one of these two treatment groups, or among patients who are exposed to the intervention as intended. The electronic health record will document each of these safety outcomes as they occur over the course of the study. Because these are more likely to be documented in outpatient than inpatient settings the lag between occurrence and documentation will be minimal.

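### The safety lists and Table 4 do not provide for deaths, hospitalizations or emergency visits by arm, although the plan says medication events can be severe or fatal

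*Combined protocol and SAP*

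**What the plan says.** Section 14.B states that the risks are chiefly "adverse events related to medications, which can potentially be severe or even fatal". It adds that "patients in the telehealth group may be treated with greater numbers and higher doses of antihypertensive therapy", and that the team's previous telehealth trial saw several more hypotension episodes in the telehealth group, a difference that was not statistically significant. It concludes that "the risks of participating in the study are considered minimal and no greater than those incurred through routine treatment of hypertension".

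The safety outcomes are described in four places:

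- Section 7.C: "laboratory abnormalities in electrolytes and kidney function that may be affected by hypertension medications, as well as low blood pressure (hypotension) and fainting".
- Section 8.A, on what the EHR tool gathers: "safety events (hypotension, fainting", with potassium, sodium and creatinine among the laboratory values.
- Section 14.C.2: monitoring for adverse effects by "extracting EHR laboratory data on potassium, sodium, and kidney function, and diagnoses for hypotension and fainting".
- Section 15, item 4.4: examples of diagnoses (hypotension or fainting, electrolyte disturbances, renal failure) and of laboratory measures (Na, K, eGFR). Vitals, diagnosis codes and lab results are extracted periodically to identify these outcomes before and after enrollment.

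Table 4 sets out what the DSMB receives. Its safety block has two rows, diagnoses and lab measures, each shown in aggregate, by treatment and as treated, over time.

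**The concern.** The plan acknowledges that drug harms can be severe or fatal and that treatment may be more intensive in one arm. The outcomes it then lists are conditions and laboratory values. It does not list the events by which severity is usually recognized: death, admission and emergency attendance. A listed diagnosis made in hospital may be counted as a diagnosis, but no row shows that it led to an admission, and a death with no listed diagnosis has no place in the table.

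Three features of the plan make this matter:

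- Under the partial consent waiver (14.C.1.a), patients do not know at the visit that their blood pressure care is linked to research. The waiver rests on risk no greater than routine care. By-arm counts of serious events are the direct check on that premise.
- Item 4.3 of section 15 declines stopping rules for benefit and for futility, and the supplied text states no threshold for harm. Periodic DSMB review of Table 4 is therefore the main safeguard.
- Patients may be as old as 85 (4.C) and are followed for 24 months, so some deaths and admissions are to be expected in both arms.

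**Working it through.** The point is mainly textual, and there is no figure in the plan to reproduce.

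**Step 1. Compare the lists.**

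| Place | Hypotension / fainting | Electrolytes | Kidney | Death, admission or emergency visit |
|---|---|---|---|---|
| 7.C | yes | labs | labs | not mentioned |
| 8.A | yes | labs | labs | not mentioned |
| 14.C.2 | yes | labs | labs | not mentioned |
| 15, item 4.4 | yes | diagnoses and labs | diagnoses and labs | not mentioned |
| Table 4 | within diagnoses row | within both rows | within both rows | no row |

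The lists in 7.C and 14.C.2 are not given as examples; those in item 4.4 are.

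**Step 2. Could another stream fill the gap?** Patient-reported side effects are collected by survey (7.B), and summaries by arm go to the DSMB in closed session (item 4.5 and Table 4). Section 10.A.3 assumes response of 60% at enrollment and 75% at 6 months. Section 8.B says enrollment non-respondents get no later surveys. If the 75% applies to enrollment respondents, 6-month coverage is 0.60 × 0.75 = 0.45 of those enrolled, or 900 of 2000. Patients who have died cannot answer. This stream cannot replace counts of deaths and admissions.

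**Step 3. Are the data at hand?** Section 14.A lists diagnoses and encounters among the EHR data, and item 4.4 already schedules a periodic safety extract. Section 14.A names pharmacy claims only, and no section names a source for vital status.

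**Step 4. Scale, for illustration only.** The documents give no event rates, so the 24-month risks below are assumptions.

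- Events = 2000 × risk.
- Smallest detectable risk ratio, 80% power, two-sided 5%: 1000 per arm divided by the design effect 1 + (100 − 1) × ICC, with 100 patients per clinic from 10.A.3.
- Power = Φ[(d − 1.96 × SE0) / SE1], where d is the risk difference, SE0 the pooled and SE1 the unpooled standard error.
- ICC 0.003 is the plan's estimate for SBP, and 0.01 and 0.03 are the ends of its planning range. Applying them to serious events is a further assumption.
- Design effects: 1.00, 1.297, 1.99 and 3.97. Effective n per arm: 1000, 771, 503 and 252.

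| Assumed risk | Events in 2000 | RR, ICC 0 | RR, ICC 0.003 | RR, ICC 0.01 | RR, ICC 0.03 |
|---|---|---|---|---|---|
| 1% | 20 | 2.69 | 3.00 | 3.67 | 5.38 |
| 2% | 40 | 2.09 | 2.27 | 2.66 | 3.62 |
| 5% | 100 | 1.62 | 1.72 | 1.92 | 2.39 |
| 10% | 200 | 1.41 | 1.47 | 1.59 | 1.87 |

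For rare events only large ratios would be detectable, so the value lies in descriptive counts by arm for the DSMB to judge.

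**The case against.** The best defense is that this is a pragmatic comparison of two accepted care models using approved drugs, that the DSMB approved the monitoring plan and the IRB granted the waiver, and that targeted monitoring of known antihypertensive effects is a reasonable choice. That is fair as a starting point. It does not explain why the serious consequences acknowledged in 14.B have no row in the table meant to compare safety by arm.

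Several stronger inferences are tempting, and the documents do not support them:

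- *That nothing beyond the listed items is monitored, or that deaths and admissions can never reach the DSMB.* Item 4.4 gives its lists as examples, vitals are extracted too, and side-effect reports by arm go to closed session. The outcome tables cited in sections 7 and 15 (Tables 1 to 3) and the appendices are not in the supplied text. What can be said is that the supplied text makes no provision.
- *That the plan justifies its list by expecting outpatient events.* The sentence "Because these are more likely to be documented in outpatient than inpatient settings the lag between occurrence and documentation will be minimal" concerns reporting delay, not the choice of outcomes.
- *That patients who die are counted as event-free, or go on contributing person-time.* Section 10.A.4 treats EHR fields as complete in the Aim 1 missing-data plan, for care processes and vital signs. It sets no rule for safety denominators, and item 4.4 leaves the metric open.
- *That only mild over-treatment is covered, or that under-treatment is invisible.* Renal failure is among the examples. SBP is the primary outcome, and clinical outcome descriptives go to the DSMB by treatment and month in closed session.
- *That 14.B rates severe or fatal events as likely.* It names medication events generally and judges the overall risk minimal.

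**Conclusion.** The point holds as a gap in provision. Section 14.B acknowledges that medication events can be severe or fatal and that telehealth treatment may be more intensive, but neither the supplied safety lists nor the Table 4 safety rows provide for all-cause deaths, hospitalizations or emergency visits by arm. Followed as written, the DSMB's safety comparison could miss an imbalance in such events.

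The size of any imbalance cannot be estimated from the documents. The 20 to 200 events in the illustration rest wholly on assumed risks of 1% to 10% and say nothing about a difference between arms. The conclusion also assumes that the outcome tables and appendices not supplied do not already add these events. The change is worth making: it adds a specific safeguard at modest cost and alters no treatment.

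**What to change.** Amend section 15, item 4.4, and the safety block of Table 4 to add, by arm, counts and rates of:

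1. all-cause death as recorded in the EHR;
2. all-cause hospitalization and all-cause emergency visits;
3. hospitalizations or emergency visits coded for syncope, fall or fracture, acute kidney injury, electrolyte disorder, stroke, MI or heart failure.

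Take the visits from the encounter and diagnosis data listed in 14.A, through the extract already planned. State that rates are calculated up to death where a death is recorded. Report the results descriptively at each DSMB meeting and in the primary outcomes paper, without formal between-arm tests for the rare events.

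The cost is a set of code lists and a monitoring-plan amendment, possibly with IRB review, because the survey agreement in 14.C.1.b covers EHR data related to hypertension. Deaths and visits outside the health system will be under-captured, since 14.A names only pharmacy claims. It should also be confirmed that the extract reaches the system's seven hospitals (4.A). The amendment and the paper should state both limits.

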#### **14.C. Adequacy of Protection Against Risks**

##### **14.C.1. Protection of Informed Consent**

###### **14.C.1.a EHR and claims data collection**

We have been granted a partial waiver of documentation of informed consent from the HealthPartners Institutional Review Board (IRB) for the collection of electronic health record and claims data following reasons:

1. The clinic-based care model is considered a standard of care and has not been shown to have any risks greater than routine care for hypertension;
2. The telehealth care intervention has been studied in multiple settings and has not been shown to have any risks greater than routine care for hypertension using current guidelines for BP control;
3. The enrollment of patients by clinic staff in the routine care setting would make it impractical to obtain informed consent; and
4. We will not require special research visits to collect data from participants and will use health data that is routinely recorded in the EHR.

This means that patients will receive care at their clinic according to their clinic's randomization status and will not be aware of any relationship between research and their clinic care for their blood pressure at the time of their clinic visit.

These conditions apply for patients until they are contacted and respond to our mailed survey. Once a patient responds to the survey, the 3rd criteria above no longer applies. Therefore we have included a question at the end of the survey to request consent to use medical record data. See Appendix H.

#### **14.C.1.b Patient Surveys**

Participants will consent to the surveys through an affirmation demonstrated by the survey completion. The first (enrollment) participant survey will be mailed to an individual patient within 1 week of the clinic visit that qualified them to be enrolled in this study (see section on surveys). That initial survey mailing will include a cover letter explaining the purpose of the survey and why that patient is receiving it. It will include all the elements of consent that would normally be included in a consent form, and an explanation that returning or completing this survey includes the patient's agreement that their responses and EHR data related to hypertension can be used for research purposes. Patients who are identified and enrolled by Wizard but who are on the HPI Exclusion List will not be sent a survey. (See Appendix H for draft survey instrument and other patient materials).

#### **14.C.1.c. Patient focus groups and HealthPartners employee interviews**

Focus group participants will be recruited from among patients completing surveys. They will undergo a documented consent process prior to participating in any focus group. During the recruitment process for participation in focus groups they will be told the basic elements of consent (e.g. time required, privacy risks, audio recording and transcription, de-identification, incentive, etc). Upon arriving to the focus group, the patient will be given time to review the entire consent form and will have an opportunity to sit privately with a research coordinator to ask any questions. Only participants who agree and consent to participate will be included in the group. Anyone who chooses to decline will be offered an incentive for their time for attending.

HealthPartners employees who may be interviewed for evaluation purposes will not be asked to sign a formal consent because their interviews will be considered part of a continuing process improvement effort in partnership with the system stakeholders invested in this project. However, these employees will be assured of their privacy and will only be interviewed upon their personal agreement.

#### **14.C.1.d. HIPAA protections**

In addition to the internal HP Institute policies, HIPAA itself makes specific provision for waiver of authorization to use PHI for research recruitment purposes under some specific conditions, all of which this study meets: "For research uses and disclosures of personal health identifiers (PHI), an IRB or privacy board may approve a waiver or an alteration of the authorization requirement in whole or in part. A complete waiver occurs when the IRB or privacy board determines that no authorization is required for a covered entity to use and disclose PHI for a particular research project. A partial waiver of authorization occurs when an IRB or privacy board determines that a covered entity does not need authorization for all PHI uses and disclosures for research purposes, such as disclosing PHI for research recruitment purposes. An IRB or privacy board may also approve a request that removes some PHI, but not all, or alters the requirements for an authorization (an alteration)." See:

[http://privacyruleandresearch.nih.gov/pr\\_08.asp#8](http://privacyruleandresearch.nih.gov/pr_08.asp#8)

